2.2 Sample Size

There is no formal assessment of sample size. The sample size of 100 subjects was chosen to ensure at least 90 subjects complete the study. The sample size is not expected to yield statistically significant results.

3.0 ANALYSIS POPULATIONS

3.1 Safety Analysis Set

The Safety Analysis Set is defined as all enrolled and randomized subjects who applied at least one treatment of the study drug.

3.2 Full Analysis Set

The Full Analysis Set (FAS) is defined as all randomized subjects who applied at least one administration of the study drug and who had at least one post-baseline efficacy assessment.

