8.3 ANALYSIS POPULATIONS

8.3.1 Intent-to-Treat Analysis Set

The Intent-to-treat (ITT) Analysis Set is defined as all subjects enrolled and randomized into the study.

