3.3 Per Protocol Analysis Set

The Per Protocol Analysis Set (PP) is defined as all randomized subjects who applied at least one administration of the study drug and who had at least one post-baseline efficacy assessment and who do not have any major protocol violations, including:

- Violations of inclusion/exclusion criteria;
- Use of prohibited concomitant medications'
- Noncompliance (i.e., less than 60% compliant with study treatment), as determined by the average product usage for the duration of participation;
- Failure to provide a clinical observation at Day 28;
- A scheduled visit occurring more than 5 days outside of the +/- 2-day visit window.

Santalis Pharmaceuticals

Protocol No. SAN007-02: Statistical Analysis Plan Implementation Document

Although non-compliance is defined in the protocol as <90% compliance with study treatment, subsequent consideration of subject medication use evaluated prior to study data unmasking lead to a reduction in the threshold to <60% compliance.

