3.4 Other Analysis Sets

An Intent-to-Treat Analysis Set (ITT) is defined as all subjects enrolled and randomized into the study. However, there is no analysis specific to the ITT population and it will not be used in the generation of any tables or listings.

The Enrolled Population is defined as all subjects who signed the informed consent. The Enrolled Population is referred to in the generation of listings and tabulation of subject disposition.

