4.1.2 Qualitative Assessments

Qualitative assessments (categorical data) will be summarized by reporting the frequency (count and percent) of subjects falling within the category. Unless specified otherwise for a particular assessment, the denominator for calculating a percentage will be the total number of subjects in the analysis population for the subgroup being analyzed; for example, within study arm, the number of subjects within the study arm in the analysis population will be the denominator. For overall summaries, the total number of subjects in the analysis population will be used as the denominator.

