4.2 Methods for Handling Missing Data

Missing efficacy data will be imputed using the last observation carried forward unless specified otherwise; unscheduled visit data will be included in the carry forward procedure. No imputations will be made for missing safety data.

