8.0 EVALUATION OF EFFICACY PARAMETERS

Analyses in this section will be based on the FAS and the PP analysis set. The primary set for efficacy analyses will be the FAS; supportive analyses will be based on the PP. All analyses will be performed by study arm with missing data imputed using the last observation carried forward.

Throughout this section the term 'follow-up visit' will refer to any post-baseline visit, whether an office visit or a telephone contact. Only safety data and status of atopic dermatitis were to be collected at the Day 35 follow-up visit.

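### No planned efficacy table counts a randomized subject without any post-baseline assessment as a non-responder, because every table uses the FAS or PP and the ITT set is unused

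*SAP*

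**What the plan says.** SAP 3.2 admits to the FAS randomized subjects "who applied at least one administration of the study drug and who had at least one post-baseline efficacy assessment". SAP 3.3 puts the same two conditions on the PP set and adds exclusions, including "Failure to provide a clinical observation at Day 28", so the PP set cannot recover anyone the FAS omits.

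SAP 8.0 states: "Analyses in this section will be based on the FAS and the PP analysis set". The FAS is primary and the PP supportive, and Table 10.2 assigns every IGA, EASI and BSA table to one or the other. Unless specified otherwise, SAP 4.1.2 makes "the denominator for calculating a percentage will be the total number of subjects in the analysis population for the subgroup being analyzed".

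Protocol 8.3.1 has a wider set: "The Intent-to-treat (ITT) Analysis Set is defined as all subjects enrolled and randomized into the study". SAP 3.4 repeats that definition but adds that "there is no analysis specific to the ITT population and it will not be used in the generation of any tables or listings".

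On missing data, SAP 4.2 says: "Missing efficacy data will be imputed using the last observation carried forward unless specified otherwise". SAP 4.1 and 4.2 bring early-termination and unscheduled assessments into the carry-forward. Neither section has a rule for a subject with nothing recorded after baseline.

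Protocol 8.3.2 defines the FAS in the same way and makes it the primary efficacy population. The protocol synopsis describes a narrower efficacy set (at least 90% of treatments by product usage), which also would not retain very early leavers.

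**The concern.** The first scheduled efficacy assessment after baseline is Day 7 (±2 days). A subject who applies the first dose in the clinic, leaves, and is not assessed again drops out of both the numerator and the denominator of every responder table. Last observation carried forward does not reach such a subject, who is outside the set before imputation starts. Protocol 6.7 also allows subjects who discontinue early to be replaced, so the gap in the efficacy data may be filled by someone else.

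What is at stake is the estimated improvement rate. Protocol 3.3 expects those rates, with the safety profile, to support the design of Phase 3 studies. A rate among subjects who came back at least once answers a different question from a rate among all randomized, and the plan produces only the first.

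**Working it through.** **The plan's own figure.** There is no power calculation to reproduce. SAP 2.2 gives 100 subjects so that at least 90 complete. This fits 10% non-completion, 90/(1 - 0.10) = 100, but the 10% comes from the pair itself, so the check is circular. It covers all arms and the whole study and is not an early-loss rate.

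**General result.** For one arm let n = randomized, m = randomized with no post-baseline efficacy assessment, r = responders.

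- Rate under the plan (FAS): r/(n-m)
- Rate with these subjects as non-responders: r/n
- Ratio: n/(n-m), above 1 whenever m > 0. The rate itself rises if r > 0.

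For n = 67, m = 1 gives 67/66 = 1.015 and m = 5 gives 67/62 = 1.081. For n = 33, m = 1 gives 33/32 = 1.031 and m = 3 gives 33/30 = 1.100.

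**Between-arm difference.** The documents give no response rate and no early-loss rate, so the inputs are assumptions: 100 subjects split 67:33 (the 2:1 ratio with both strengths pooled), 30 active and 12 placebo responders. With all randomized subjects in the denominator, 30/67 = 44.8%, 12/33 = 36.4%, difference 8.4 points. Under the FAS:

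| Losses, active / placebo | Active rate | Placebo rate | Difference (points) | Change from 8.4 |
|---|---|---|---|---|
| 0 / 0 | 30/67 = 44.8% | 12/33 = 36.4% | 8.4 | 0 |
| 1 / 0 | 30/66 = 45.5% | 12/33 = 36.4% | 9.1 | +0.7 |
| 2 / 0 | 30/65 = 46.2% | 12/33 = 36.4% | 9.8 | +1.4 |
| 6 / 0 | 30/61 = 49.2% | 12/33 = 36.4% | 12.8 | +4.4 |
| 8 / 0 | 30/59 = 50.8% | 12/33 = 36.4% | 14.5 | +6.1 |
| 6 / 3 | 30/61 = 49.2% | 12/30 = 40.0% | 9.2 | +0.8 |
| 0 / 3 | 30/67 = 44.8% | 12/30 = 40.0% | 4.8 | -3.6 |

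Losses in proportion to arm size multiply both rates by nearly the same factor (67/61 = 1.098 and 33/30 = 1.100), so the difference is only scaled up by about a tenth. Losses confined to one arm move it most, in the direction of that arm.

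**Smaller arms.** The pooled active arm of 67 is not a planned display. SAP 8.0 analyses by study arm, and SAP 10.1.2 lists 10%, 5% and placebo separately. In an assumed arm of 33, one lost subject moves the rate from 16/33 = 48.5% to 16/32 = 50.0%, or 1.5 points.

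**The case against.** A reader might infer that the plan favours active drug, since local reaction is an expected risk and would drive early loss there. The documents do not support that step.

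- They report no early loss by arm. Placebo subjects may also leave early, for lack of effect for example, and that would push the difference the other way.
- Much of the proposed mechanism is covered. Protocol 7.1.4 sends a subject with a new or worsening rash to the site for examination. Protocol 6.5 asks for every effort at a final evaluation, and 6.6 makes the withdrawal procedures those of the last visit, which include IGA, EASI and BSA. SAP 4.1 and 4.2 then use exit and unscheduled data. A subject who reacts and is assessed before Day 7 stays in the FAS. The cover is not complete: 7.1.4 does not itself require IGA or EASI at that examination, and 6.5 is an effort, not a guarantee.
- Losses may be few. The sponsor's wart study at 10% to 30% EISO (Protocol 1.1), in a different population, had 183 completers and one discontinuation for a drug-related adverse event. Eight unassessed losses on active before Day 7 would be most of the roughly ten non-completers the plan allows for in total.

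A reader might also infer that the SAP departs from the protocol. It does not. The protocol makes the FAS primary for efficacy and assigns no efficacy analysis to the ITT set.

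The exclusions are also partly visible. SAP 5.1 tabulates FAS counts and discontinuation reasons by arm, and Listing 16.2.1.2 covers evaluability, so a reader could rebuild r/n by hand. The IGA clear or almost clear endpoint is worded as a number of subjects, and that count does not depend on the denominator, although SAP 8.1 reports the percentage as well. Finally, efficacy is preliminary and descriptive, safety is primary, and no test is planned.

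These points limit direction, size and stakes. They do not supply an efficacy table on all randomized subjects.

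**Conclusion.** The point holds as a gap in the planned displays. Any arm with m > 0 and at least one responder shows a responder rate n/(n-m) times the rate obtained when subjects without a post-baseline assessment count as failures. This follows from the definitions and needs no assumption about the data.

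The effect on the comparison is undetermined. Under the assumed 67:33 split with 30 and 12 responders it runs from 0 to +6.1 points for 0 to 8 losses on active only, is +0.8 points for 6 and 3 losses, and is negative for losses on placebo only. If everyone has a post-baseline assessment, the effect is nil. A systematic bias towards active is not shown. The consequence is for estimates that may feed Phase 3 planning, not for a type I error rate. It merits an inexpensive supportive analysis, not a change of primary population.

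**What to change.** Keep the FAS as the primary efficacy set.

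1. In SAP 8.0 and Table 10.2, add supportive tables by study arm on the ITT set for the five responder endpoints: EASI reduction of at least 25%, EASI reduction of at least 50%, IGA clear or almost clear, IGA improvement of at least one grade, and BSA reduction of at least 20%. Count subjects with no post-baseline efficacy assessment as non-responders.
2. Amend SAP 3.4, which now bars any use of the ITT set. Say that a randomized subject who was never treated is shown in the assigned arm, since the as-treated rule in SAP 3.5 gives no arm for that subject.
3. In Table 14.1.1, which already gives FAS counts by arm, add the reason for exclusion from the FAS and use randomized subjects as the denominator. SAP 5.1 now bases percentages on everyone who signed consent.

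The cost is SAP wording and a few extra tables, with no new data and no change to conduct. Responder rates in the added tables will be slightly lower than in the FAS if anyone was lost early. If nobody was, the two sets of tables will agree.

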3.3 Per Protocol Analysis Set

The Per Protocol Analysis Set (PP) is defined as all randomized subjects who applied at least one administration of the study drug and who had at least one post-baseline efficacy assessment and who do not have any major protocol violations, including:

- Violations of inclusion/exclusion criteria;
- Use of prohibited concomitant medications'
- Noncompliance (i.e., less than 60% compliant with study treatment), as determined by the average product usage for the duration of participation;
- Failure to provide a clinical observation at Day 28;
- A scheduled visit occurring more than 5 days outside of the +/- 2-day visit window.

Santalis Pharmaceuticals

Protocol No. SAN007-02: Statistical Analysis Plan Implementation Document

Although non-compliance is defined in the protocol as <90% compliance with study treatment, subsequent consideration of subject medication use evaluated prior to study data unmasking lead to a reduction in the threshold to <60% compliance.

3.4 Other Analysis Sets

An Intent-to-Treat Analysis Set (ITT) is defined as all subjects enrolled and randomized into the study. However, there is no analysis specific to the ITT population and it will not be used in the generation of any tables or listings.

The Enrolled Population is defined as all subjects who signed the informed consent. The Enrolled Population is referred to in the generation of listings and tabulation of subject disposition.

3.5 Treatment Assignment

For all analysis sets described above, subjects will be analyzed as treated. Mis-randomizations that resulted in subjects receiving an incorrect treatment will not be reassigned. These subjects will be noted in the clinical study report.

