8. STATISTICAL METHODS AND DETERMINATION OF SAMPLE SIZE

8.1 GENERAL CONSIDERATIONS FOR DATA ANALYSIS

- Up to 100 subjects will be enrolled in this study to ensure 90 subjects complete the study, from the time of this amendment. The primary endpoint of this study is to determine the safety profile of SAN007 by evaluating AEs, with respect to severity, duration, and relationship to the study drug, as well as tolerability by subjects reporting discomfort during or immediately following an application of SAN007. The preliminary efficacy analysis of the study will be evaluated using the following:
- Percentage of subjects who have a ≥ 25% reduction in the Eczema Area and Severity Index (EASI) score at any point during the trial.
- Number of subjects achieving an Investigator Global Assessment (IGA) of "clear" or "almost clear" at any time point during the 28 days of therapy. The study restricted treatment areas are not to be included in this evaluation. (see #12 under Inclusion Criteria)
- Percentage of subjects who have a ≥50% reduction in the Eczema Area Severity Index (EASI) score at any point during the trial.
- Percentage of subjects achieving at least a 1-grade improvement in IGA score
- Percentage of subjects who have at least a 20% reduction in BSA affected by atopic dermatitis.

No interim or subgroup analyses are planned.

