8.3.2 Full Analysis Set

The Full Analysis Set (FAS) is defined as all randomized subjects who applied at least one administration of the investigative study drug, and who had at least one post-baseline efficacy assessment.

The FAS will be the primary population used for efficacy analysis.

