8.3.3 Per Protocol Set

The Per Protocol Analysis Set (PP) is defined as all subjects in the FAS who do not have any major protocol violations, including:

- Violations of inclusion/exclusion criteria;
- Use of prohibited concomitant medications;
- Noncompliance (i.e., <90% compliant with study treatment);
- Failure to provide a clinical observation at Day 28;

The PP Analysis Set will be a secondary population used for supportive analysis of efficacy variables and will be analyzed according to the study treatment actually received.

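### SAP 3.5 groups the primary efficacy set as treated, so no planned efficacy table groups subjects by randomised arm (minor).

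*SAP*

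**What the plan says.** SAP 3.5 sets one grouping rule for everything: "For all analysis sets described above, subjects will be analyzed as treated". It continues: "Mis-randomizations that resulted in subjects receiving an incorrect treatment will not be reassigned", and adds that these subjects will be noted in the clinical study report.

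The FAS is defined above that rule, in SAP 3.2, as "all randomized subjects who applied at least one administration of the study drug" and who had at least one post-baseline efficacy assessment. SAP 8.0 says: "The primary set for efficacy analyses will be the FAS; supportive analyses will be based on the PP". It has all efficacy analysed by study arm. Protocol 8.3.2 agrees: "The FAS will be the primary population used for efficacy analysis". It gives no rule for the arm in which an FAS subject is counted.

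The protocol states such a rule only for the PP set, which "will be analyzed according to the study treatment actually received" (Protocol 8.3.3).

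The one set defined purely by randomisation is not used. SAP 3.4 says of the ITT set that "there is no analysis specific to the ITT population and it will not be used in the generation of any tables or listings".

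**The concern.** In a randomised, placebo-controlled trial, the primary efficacy set is normally grouped by assigned arm, because that grouping keeps the comparison that randomisation created. Under SAP 3.5, a subject who received the wrong cream is counted with the arm whose cream was received. The PP tables cannot serve as a check, because they use the same grouping.

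The by-arm response rates are at stake. Protocol 3.3 says the study may provide estimates of improvement rates and expects Phase 3 studies to be developed from those rates and the safety profile. No test or confidence interval is planned for efficacy, so nothing beyond the descriptive estimates is affected. As-treated grouping suits the Safety set, and the protocol specifies it for PP. The concern is confined to efficacy on the FAS.

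**Working it through.** **1. Which efficacy tables group subjects as randomised?** Count by population in SAP Table 10.2:

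| Endpoint | Table numbers | Tables | FAS | PP | ITT |
|---|---|---|---|---|---|
| IGA | 14.2.2.1.1 to 14.2.2.3.2 | 6 | 3 | 3 | 0 |
| EASI | 14.2.3.1.1 to 14.2.3.4.2 | 8 | 4 | 4 | 0 |
| BSA | 14.2.4.1.1 to 14.2.4.4.2 | 8 | 4 | 4 | 0 |
| Total | | 22 | 11 | 11 | 0 |

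SAP 3.5 covers both FAS and PP, so 0 of 22 tables are grouped as randomised. Two further FAS tables, 14.2.1.1.1 (visit compliance) and 14.2.1.2.1 (product compliance), are not efficacy tables. They bring the FAS total to 13.

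**2. Does the wording leave doubt?** Read alone, the sentence on mis-randomisations could mean that such a subject stays in the randomised arm. The sentence before it says subjects are analysed as treated, so the more natural meaning is that they are not moved back to the randomised arm. The text does not settle this expressly.

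**3. How much can one subject matter?** The documents give neither FAS arm sizes nor the number of subjects affected, so all counts here are assumptions.

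Illustration: 67 active (doses pooled) with 40 responders, and 33 placebo with 13 responders. One subject was randomised to placebo but received active.

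- As randomised: 40/67 - 13/33 = 59.7% - 39.4% = 20.3 points.
- As treated, if the subject is a responder: 41/68 - 12/32 = 60.3% - 37.5% = 22.8 points, a shift of +2.5.
- As treated, if the subject is a non-responder: 40/68 - 13/32 = 58.8% - 40.6% = 18.2 points, a shift of -2.1.

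With 60 active (36 responders) and 30 placebo (12 responders), the same steps give 20.0 points as randomised and shifts of +2.7 and -2.4. With three such subjects in the 67/33 case, all responders or all non-responders, the shifts are +7.8 and -6.5.

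**4. Bound that does not depend on response rates.** Adding one subject to an arm of n changes its rate by at most 1/(n+1); removing one changes it by at most 1/n. The difference therefore moves by at most 1/(n₁+1) + 1/n₂, where n₁ is the receiving arm and n₂ the arm left.

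- 67 and 33: 1/68 + 1/33 = 1.5 + 3.0 = 4.5 points.
- 20 and 20: 1/21 + 1/20 = 4.8 + 5.0 = 9.8 points.
- 33 and 33: 1/34 + 1/33 = 2.9 + 3.0 = 6.0 points.
- 50 and 50: 1/51 + 1/50 = 2.0 + 2.0 = 4.0 points.

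Showing the 5% and 10% arms separately makes the active arms smaller and the possible shift larger. In the other direction, the FAS may exceed 100. Protocol 8.1 counts only from the amendment onward ("Up to 100 subjects will be enrolled in this study to ensure 90 subjects complete the study, from the time of this amendment"), whereas SAP 3.2 takes all randomised subjects who meet the FAS definition, and SAP 2.1 describes 5%/placebo as the original randomisation.

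**The case against.** The strongest reply is that this is a prespecified choice in a small descriptive trial whose primary objective is safety. The protocol gives no grouping rule for the FAS, the sample size is not expected to yield statistically significant results, affected subjects will be noted in the study report, and IGA, EASI and BSA values appear in by-subject listings. All of that is true. It keeps the point minor, but it does not give the primary efficacy set a randomised grouping.

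A second reply is that regrouping would not fully restore a randomised comparison. This also stands. SAP 2.1 describes two separate 2:1 randomisations, with 10%/placebo introduced at new sites or after 5%/placebo was complete at a site, so some sites contribute only one dose. The listing sort order has a single placebo group. The table shells are not available, so pooled placebo columns are an inference; if placebo is pooled, contrasts between arms are not purely randomised even with every subject in the assigned arm. The FAS also depends on events after randomisation (an application and a post-baseline assessment).

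A third reply concerns scope: grouping the whole FAS by randomised arm would also regroup the two FAS compliance tables and report product use under an arm whose product the subject did not receive. This is right, and the fix is limited to efficacy for that reason.

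**Conclusion.** The point holds and is minor. SAP 3.5 applies as-treated grouping to the primary efficacy set without giving a reason, and 0 of 22 efficacy tables keep the randomised grouping. If every subject received the assigned treatment, the two groupings agree and nothing changes. If one did not, the between-arm difference moves by about -2.1 to +2.5 points on the assumed 67/33 split and response counts. Several such subjects with the same outcome would move it further.

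Three stronger readings are tempting, and the documents do not support them:

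- A reader might infer that the SAP contradicts the protocol. It does not, because the protocol is silent on grouping for the FAS.
- A reader might infer that the results favour active treatment. Nothing in the documents links treatment errors to response, and the illustration moves the difference both ways.
- A reader might infer that subjects were in fact given the wrong treatment. SAP 3.5 only provides for that case and gives no number.

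**What to change.** Reword SAP 3.5 along these lines: *Efficacy analyses on the FAS: by randomised treatment. Safety and PP analyses, and exposure and product-compliance summaries: by treatment actually received.* Replace the clause that mis-randomised subjects are not reassigned with a statement of the arm in which they are counted in each analysis. Keep the commitment to note them in the study report. Show FAS efficacy as treated as a sensitivity analysis only if such a subject exists.

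The cost is one or two sentences in the SAP and one treatment variable in the programs for the 11 FAS efficacy tables. The two FAS compliance tables (14.2.1.1.1 and 14.2.1.2.1) stay as treated, and no new data are needed.
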